10.3 Selection of Doses in the Study

10.3.1 Selection and timing of dose for each patient

Each patient will start treatment with 50 mg zamicastat once daily (Dose A) at visit A1 and will be up-titrated step by step to the individual HTD i.e. up to 200 mg zamicastat once daily. The 100 mg tablet has to be split at the break score in two equal halves using a pill splitter.

Table 2: Dosage regimen

	Daily dose
Dose A	50 mg (half a tablet of 100 mg)
Dose B	100 mg (one tablet of 100 mg)
Dose C	150 mg (one and a half tablet of 100 mg)
Dose D	200 mg (two tablets of 100 mg)

Each next dose will start after 14 days of treatment if the previous dose was considered safe by the investigator. The up-titration is based on the following safety criteria, including but not limited to:

- Absence of symptomatic and/or clinically relevant orthostatic hypotension
- SBP > 95 mmHg or DBP > 50 mmHg
- Absence of clinically significant changes in ECG parameters (heart rate, P-R interval, QRS duration, QT and QTc interval)
- Absence of clinically significant hypersensitivity/skin allergic reactions

Patients not fulfilling the criteria for up-titration after 14 days of treatment with 50 mg zamicastat have to be withdrawn from the trial.

If the patient's next dose will not be tolerated by the patient, the dose has to be down-titrated to his/her previous dose and this dose will be considered as the individual HTD, if tolerated by the patient. Treatment at the individual HTD will be for 42 days during the maintenance period.

Zamicastat has to be taken in the morning after breakfast. The patient must not take the tablet at home on visit days (A3/B3/C3/D3, MPV1, MPV2 and MPV3).

In case a patient missed to take the dose after breakfast, (s)he should take the dose after lunch. The next dose should be taken as scheduled. If the dose was missed after lunch too, the dose for this day has to be skipped.

Patients taking 150 mg or 200 mg of zamicastat and who will not participate in the extension study will take 100 mg zamicastat for 14 days.

In case a patient will discontinue the trial early due to the occurrence of an AE, down-titration is not mandatory, but at the investigator's discretion. In case down-titration is recommended by the investigator, it should follow the same procedure as described above.

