**Table 1: Dosage regimen**

Daily dose	
Dose A	50 mg (half a tablet of 100 mg)
Dose B	100 mg (one tablet of 100 mg)
Dose C	150 mg (one and a half tablet of 100 mg)
Dose D	200 mg (two tablets of 100 mg)

Each next dose will start after 14 days of treatment if the previous dose was considered safe by the investigator. The up-titration is based on the following safety criteria, including but not limited to:

- Absence of symptomatic and/or clinically relevant orthostatic hypotension
- SBP > 95 mmHg or DBP > 50 mmHg
- Absence of clinically significant changes in ECG parameters (heart rate, P-R interval, QRS duration, QT and QTc interval)
- Absence of clinically significant hypersensitivity/skin allergic reactions

Patients not fulfilling the criteria for up-titration after 14 days of treatment with 50 mg zamicastat have to be withdrawn from the study.

If the patient's next dose will not be tolerated by the patient, the dose has to be down-titrated to his/her previous dose and this dose will be considered as the individual HTD, if tolerated by the patient. Treatment at the individual HTD will be for 42 days during the maintenance period.

Zamicastat has to be taken in the morning after breakfast. The patient must not take the tablet at home on visit days (A3/B3/C3/D3, MPV1, MPV2 and MPV3).

Patients taking 150 mg or 200 mg of zamicastat and who will not participate in the extension study will take 100 mg zamicastat for 14 days.

In case a patient will discontinue the study early due to the occurrence of an AE, down-titration is not mandatory, but at the investigator's discretion.

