## 5.4.2 Compliance

The following compliance-related data will be collected in the eCRF:

- date of IMP dispensation
- prescribed IMP dose
- number of tablets dispensed
- dispensed IMP bottle number
- toleration of IMP dose (Yes, No)
- date of IMP down-titration
- date of IMP return
- number of tablets returned
- returned IMP bottle number

The calculation of the compliance will be based on the total number of tablets prescribed, dispensed and returned overall or during particular study period (for definitions of study periods, see Section 4.6).

The total number of tablets prescribed will be calculated as the prescribed daily number of tablets based on the dose (see Section 2.5) multiplied by the length of the dose prescription in calendar days. The total number of prescribed tablets will be adjusted in the case of occurrence of adverse events with associated IMP interruption periods.

The total number of tablets dispensed and returned will be calculated as the sum of all tablets dispensed and all tablets returned during the corresponding study period. The total number of tablets returned will be considered as missing if not all dispensed bottles are returned in the same corresponding period or the returned bottle(s) is from the previous period.

The overall compliance and compliance during each treatment period will be calculated as:

$$\text{Compliance (\%)} = \frac{100 \times (\text{tablets dispensed} - \text{tablets returned})}{\text{tablets prescribed}}$$

In case an IMP bottle is not returned, the overall compliance will be considered as missing.

The following statistical output will be provided:

Table 15.1.9.2.1 Compliance (%) – Safety Set

Table 15.1.9.2.2 Compliance (%) – Full Analysis Set

Table 15.1.9.2.3 Compliance (%) – Pharmacokinetic Analysis Set

The default summary statistics of compliance will be presented by HTD and overall for the respective analysis set. Number and percentage of patients will also be summarised by compliance categories (< 90%, ≥ 90% and ≤ 110%, >110%) for the respective analysis set.

Listing 16.2.2.1 Drug Accountability – Safety Set

Information related drug accountability will be listed for the patients from the safety set.

Listing 16.2.2.2 Exposure to IMP and Compliance – Safety Set

Information related exposure to IMP and compliance will be listed for the patients from the safety set.

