## Additional Study Conduct Deviations

No.	Deviation	Major/ Minor/ Case by case review
PD#23.	Down-titration dose not according to the protocol.	Case by case
PD#24.	Up-titration safety criteria deviations	Minor
PD#25.	IMP compliance <90% or >110% by period or overall	Case by case
PD#26.	Schedule deviations of visits with scheduled IMP dispensations	Case by case
PD#27.	Time deviations of scheduled assessments (ECG, Vital signs, blood withdrawal for PK/PD) at A1 and MPV3	Case by case
PD#28.	Deviations in sequences of assessments/tests/procedures	Minor
PD#29.	Prohibited medications/therapies	Case by case
PD#30.	Adverse events with possible impact on primary endpoint.	Case by case
PD#31.	Missing/incomplete blood withdrawal for PK, blood and urinalysis sampling for PD	Case by case
PD#32.	Missing/incomplete test/examination assessments: vital signs, physical measurements, NYHA/WHO functional class, laboratory tests, physical examination, ECG, number of digital scars, modified Rodnan Skin Score, SF-36v2, 6-min walk test, echocardiography, right heart catheterisation, blood withdrawal biomarker	Minor
PD#33.	Protocol deviations documented by CRAs and selected by medical monitors for discussion during DR	Case by case

Reference listings will be made available to help with the review of the protocol deviations. The specific content and format of listings to be reviewed during the DR meeting (including any additional requirements that may be necessary to aid in review) will be determined outside the scope of this SAP.

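### For patients who reach 200 mg, overall tablet-count compliance hides dosing errors at the lower steps, and the by-period check that should show them comes out missing as the return rule is written

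*SAP*

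**What the plan says.** SAP 5.4.2 works in tablets: "The calculation of the compliance will be based on the total number of tablets prescribed, dispensed and returned overall or during particular study period". The number prescribed is the "prescribed daily number of tablets based on the dose (see Section 2.5) multiplied by the length of the dose prescription in calendar days", and SAP Table 1 sets 0.5, 1, 1.5 and 2 tablets a day for Doses A to D. The ratio is tablets dispensed minus tablets returned, over tablets prescribed, and it is used at two levels: "The overall compliance and compliance during each treatment period will be calculated as". The reporting rule is: "Number and percentage of patients will also be summarised by compliance categories (< 90%, ≥ 90% and ≤ 110%, >110%) for the respective analysis set". In SAP Section 6, PD#25 sends "IMP compliance <90% or >110% by period or overall" to case-by-case review.

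Three further provisions matter here:

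- **Periods.** SAP 4.6 gives each dose its own toleration period. It opens with the on-site intake at A1, A3, B3 or C3 and closes the day before A3, B3, C3 or D3, or the day before a down-titration.
- **Returns.** SAP 5.4.2 treats a period's returns as missing when a bottle dispensed in that period comes back outside it, or when a returned bottle belongs to the preceding period. Under Protocol 10.7 and 11.6.4, bottles are handed in and counted at the on-site visits.
- **Halving.** Protocol 10.3.1 says: "The 100 mg tablet has to be split at the break score in two equal halves using a pill splitter". Protocol 10.5 sizes each supply for two tablets a day.

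**The concern.** Summing tablets over doses that differ fourfold in tablets per day lets the 200 mg days dominate the total. An error confined to an early step is diluted, and errors in opposite directions can cancel.

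The early steps matter because the trough concentration at steady state for each dose is a primary endpoint (Protocol 13.1.1). Protocol 6.2.2 describes steady state by Day 3 to 5 and dose-linear pharmacokinetics from 25 to 400 mg. On those statements, a patient who took whole tablets throughout the 50 mg step would contribute a trough of about twice the 50 mg value, labelled as 50 mg. Tolerability by dose would be mislabelled in the same way.

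There is no patient diary (Protocol 15.2), and the intake records listed in SAP 5.4.1 concern when drug was taken. The tablet count is therefore the main evidence of how much was taken at home.

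**Working it through.** **Schedule check.** The documents give no tablet total, but the Protocol synopsis states up to 124 treatment days for a patient tolerating 200 mg. With every visit at the late edge of its window, the last day is 1 + 4×16 + 43 + 16 = Day 124, which matches. The nominal schedule to the end of maintenance is 4×14 + 42 = 98 days.

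**Prescribed tablets, 200 mg reached, nominal schedule.** 14×0.5 + 14×1 + 14×1.5 + 56×2 = 7 + 14 + 21 + 112 = 154.

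**Overall compliance = 100 × used / 154**

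| Behaviour | Tablets used | Overall | Range over visit windows |
|---|---|---|---|
| Never halves (1 tablet for 50 mg, 2 for 150 mg) | 14+14+28+112 = 168 | 109.1% | 107.5-110.8% |
| Whole tablets in the 50 mg step only | 154+7 = 161 | 104.5% | 103.6-105.6% |
| Misses the 50 mg step | 154−7 = 147 | 95.5% | 94.4-96.4% |
| Misses the 100 mg step | 154−14 = 140 | 90.9% | 88.9-92.7% |

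The ranges use steps of 12 to 16 days and maintenance of 40 to 44 days. The extremes of the second row are 1 + 6/166 and 1 + 8/142. All four nominal values lie in the 90-110% class. One whole tablet a day at both 50 mg and 150 mg gives 14+14+14+112 = 154 tablets, or exactly 100.0%. Each step opens with an on-site dose, so missing 13 of 14 days is more realistic than missing all 14. It gives 95.8% (50 mg) and 91.6% (100 mg), the same class.

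**Lower highest tolerated doses** (1 to 14 days on the failed next dose, no final down-titration):

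| Highest tolerated dose | Never halves | Misses 50 mg step | Misses 100 mg step |
|---|---|---|---|
| 150 mg | 126-133% | 93.5-94.7% | 86.9-89.5% |
| 100 mg | 112-117% | 89.1-91.7% | 78-83% |
| 50 mg | 167-197% | 76-83% (initial step) | not assessed |

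With the 14-day down-titration, missing the 100 mg step at 150 mg reaches at most 90.5%.

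**Whether the by-period value is available.** Take a bottle dispensed at A1. The 50 mg toleration period ends the day before A3. A2 is a telephone contact, so the bottle comes back at A3, which is the first day of the 100 mg period.

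- The bottle was not returned within the 50 mg period, so the 50 mg value is missing.
- It reaches the 100 mg period as a bottle from the period before. The same happens at B3 and C3.
- Bottles dispensed at C3 come back at D3. This removes the total for the whole dose finding period, and the maintenance period then receives a bottle from the period before.

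Read literally, the rule leaves no by-period value for any dose-finding step that runs to its scheduled visit, nor for the maintenance period after D3.

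**If the whole dose finding period is scored with the return rule relaxed.** Prescribed: 7+14+21+28 = 70. Missing 50 mg gives 63/70 = 90.0% and whole tablets at 50 mg give 77/70 = 110.0%. Both stay in the class because its limits are inclusive. Never halving gives 84/70 = 120% and missing 100 mg gives 56/70 = 80%.

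**If each dose level is scored.** Whole tablets give 14/7 = 200% at 50 mg and 28/21 = 133% at 150 mg. A missed step gives 0%.

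**The case against.** The strongest reply is that the SAP already has the remedy. It calculates compliance by period, defines a period for each dose, and words PD#25 so that one out-of-range period is enough. That is clearly the intent, and it would work if the values could be computed. Under the return rule they cannot, and the SAP does not say which periods feed the category table.

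Other objections stand in part:

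- A reader might infer that any patient who never halves a tablet is classed as compliant. The documents do not support this. At every lower highest tolerated dose the overall figure exceeds 110%, and even at 200 mg some permitted visit timings give 110.8% or 88.9%.
- PD#25 is not the only safeguard. PD#23, PD#26 and PD#33, the monitor's accountability checks (Protocol 15.3) and Listings 16.2.2.1 and 16.2.2.2 also exist. None of them sets a rule on quantity taken per dose.
- Missed steps are a weak route to a wrong trough, because Protocol 11.2.1 moves the sample to the next day if the previous day's tablet was not taken. That rule does not protect against whole-tablet use.
- A reader might conclude that the overall figure should be counted in daily doses. That total also dilutes errors: whole tablets at 150 mg only give (84 + 28/1.5)/98 = 102.67/98 = 104.8%.

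**Conclusion.** The concern holds for the overall figure in patients who reach 200 mg. On the nominal schedule, gross errors at 50 mg or 100 mg leave it between 90.9% and 109.1%, inside the accepted class. Visit timing can push never halving or a missed 100 mg step just outside, but errors confined to the 50 mg step stay inside throughout. At lower doses most of these errors are flagged; the clear exception is a missed 50 mg step at 150 mg.

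What makes this more than a weighting preference is that the period definitions and the return rule together leave the by-period values missing.

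The figures assume that never halving means rounding up, that every bottle is eventually returned (otherwise the overall figure is missing too), and that there are no interruptions for adverse events. It should not be inferred that the primary pharmacokinetic results will be wrong. PD#25 is decided case by case, the pharmacokinetic analysis set is defined in a separate plan, and the layout of Table 15.1.9.2 is in table shells; neither of those documents was available.

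**What to change.** In SAP 5.4.2:

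1. Assign each returned bottle, by bottle number, to the dose level for which it was dispensed, rather than to the period containing its return date. Prescribed dose, dispensed and returned bottle numbers and the down-titration date are already collected.
2. Where a bottle spans a down-titration, split it at the recorded date. If the down-titration was made by telephone there is no tablet count on that day, so state how the used tablets are divided, or report one value for that bottle.
3. Compute compliance per dose level and apply the three categories to those values in Tables 15.1.9.2.1 to 15.1.9.2.3.
4. Apply PD#25 to the dose-level values as well as to the overall figure.

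The overall tablet-based figure can stay as a descriptive summary.

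The cost is revised wording, minor programming and probably more patients for case-by-case review. The SAP cites a Data Review Report dated 10 March 2022, so any newly flagged patient would need a documented addition to that review. No dosing or data collection changes.

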10.7 Treatment Compliance and Drug Accountability

At each study visit, the patient will be reminded of the importance of taking the IMP exactly as prescribed. IMP is to be taken by study patients only, during the course of the study. Study staff will dispense the appropriate amount of IMP for each patient and for each treatment interval plus additional medication. At each on-site visit, patients must bring back the IMP

(including empty and partially empty containers) and drug accountability must be performed and documented.

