### Dose finding period

The dose finding period will be defined as the period from the date of the first IMP intake to the day before visit D3 or the day before IMP down-titration.

The dose finding period will be split into **dose toleration periods** for each dose prescribed for that period. The period will start from the date of the IMP taken at the site at visit A1/A3/B3/C3 to the day before visit A3/B3/C3/D3 or the day before IMP down-titration.

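### As written, the SAP compliance rule leaves dose-finding compliance missing for essentially every patient who finishes a dose period, because bottles come back one day after the period ends

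*SAP*

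**What the plan says.** **Counting rule.** SAP 5.4.2 takes tablets dispensed minus tablets returned, divided by tablets prescribed, overall and for each treatment period as defined in SAP 4.6. "The total number of tablets returned will be considered as missing if not all dispensed bottles are returned in the same corresponding period", and the same sentence continues "or the returned bottle(s) is from the previous period". Overall compliance has a separate rule: "In case an IMP bottle is not returned, the overall compliance will be considered as missing".

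**Period limits (SAP 4.6).** For each dose: "The period will start from the date of the IMP taken at the site at visit A1/A3/B3/C3 to the day before visit A3/B3/C3/D3". When a patient is down-titrated, the dose period likewise closes one day earlier than the down-titration. The whole dose finding period ends on the day before D3 or the day before down-titration. Maintenance starts at D3 or at down-titration and includes the first day of MPV3 (for extension patients, it runs to the end date of MPV3). The down-titration period runs from the second day of MPV3, or the day after EDV, to FUV1. For patients who discontinue early, the EDV date closes whichever period is ongoing.

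**Returns.** Protocol 10.7: "At each on-site visit, patients must bring back the IMP". In the schedule of procedures, IMP accountability first appears at A3/B3/C3/D3. A2/B2/C2/D2 and FUV1 are telephone contacts. Down-titration bottles are accounted for at the final FU visit (Protocol 11.6.9).

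**Use.** SAP 6 lists deviation PD#25, reviewed case by case: "IMP compliance <90% or >110% by period or overall".

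**The concern.** The counting rule asks for bottles to be back inside a period that closes before the first scheduled visit at which they can be handed back. If so, a stated rule, not poor adherence or poor record keeping, removes most by-period compliance values.

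The trough concentration at each dose is part of the primary PK endpoint. The study has no patient diary (Protocol 15.2), so tablet counts are the main evidence of multi-day adherence at each dose level. By-period compliance is also one of the two arms of PD#25, which feeds the review of deviations that may affect PK.

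**Working it through.** The documents give no figure to reproduce, so the check is a dated trace.

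**Inputs.** Nominal visit days from the schedule: A1 = 1, A3 = 15, B3 = 29, C3 = 43, D3 = 57, MPV1 = 70, MPV2 = 84, MPV3 = 98–99. Each bottle is dispensed at one on-site visit and returned at the next. Period limits are from SAP 4.6. The ±2-day visit windows change nothing, because the limit moves with the visit.

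**Rule.** Clause 1: the period is missing if any bottle dispensed in it is not returned in it. Clause 2, read literally: the period is also missing if a bottle returned in it comes from the previous period.

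**Patient completing 200 mg and entering the extension**

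| Period | Days | Bottles dispensed in it | Returned on day | Clause 1 | Clauses 1 and 2 |
|---|---|---|---|---|---|
| A | 1–14 | A1 | 15 | missing | missing |
| B | 15–28 | A3 | 29 | missing | missing |
| C | 29–42 | B3 | 43 | missing | missing |
| D | 43–56 | C3 | 57 | missing | missing |
| Whole dose finding | 1–56 | A1, A3, B3, C3 | 15, 29, 43, 57 | missing (C3 bottle only) | missing |
| Maintenance | 57–99 | D3, MPV1, MPV2 | 70, 84, 98 | calculable | missing (C3 bottle returned on day 57) |

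Of 7 scheduled returns, 4 (A3, B3, C3, D3) fall in the next dose or maintenance period and 3 (MPV1, MPV2, MPV3) fall in the same period. Of the 6 values above, 5 are missing on either reading; the sixth depends on clause 2.

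**Other paths**

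- *Down-titrated during dose C, on site or by telephone, on day 35.* Periods A, B, C (29–34) and whole dose finding (1–34) fail clause 1. Maintenance passes clause 1 and fails clause 2 if that is literal, because the dose C bottle comes back on day 35 (on site) or at MPV1 (telephone).
- *Down-titration period, no extension.* If the bottle is recorded as dispensed on the second day of MPV3, it comes back at the final FU visit after the period closed at FUV1, so the period is missing. If it is recorded on the first day, it counts as a maintenance bottle: maintenance then fails clause 1, and the down-titration period has no dispensed tablets, so it has no meaningful value.
- *Withdrawn in dose A, bottle returned at EDV on day 10.* Period A and whole dose finding are calculable.
- *Withdrawn in dose B, returned at EDV on day 20.* Period A is missing; B passes clause 1 and fails clause 2 if literal; whole dose finding is calculable.

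**Check of the remedy.** Credit each return to the period of dispensing. Assume the dose taken at a closing visit comes from the new bottle. A fully adherent patient then has 14 × 0.5 = 7, 14 × 1 = 14, 14 × 1.5 = 21 and 14 × 2 = 28 tablets used against the same numbers prescribed: 100% in each of A to D.

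One case breaks this. Assume a telephone down-titration after 7 days of dose C, with no new bottle until MPV1 13 days later. The B3 bottle supplies 7 × 1.5 + 13 × 1 = 23.5 tablets. This is feasible, since supply for 14 days at the highest dose is 14 × 2 = 28. Crediting all of it to dose C gives 23.5 / (7 × 1.5) = 23.5 / 10.5 = 224%, a false value above 110%. Over the combined interval it is 23.5 / (10.5 + 13) = 100%.

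**The case against.** The best defence is that the damage is limited. Returns of maintenance bottles at MPV1 to MPV3 and returns at EDV do fall inside the ongoing period, and A3, B3 and C3 returns fall inside the whole dose finding period. Overall compliance does not depend on period limits. PD#25 is a case-by-case review item, not an automatic exclusion. The PK analysis set is defined in a separate plan that is not among these documents. Dosing just before a trough is checked directly: the time of the previous dose is recorded, and sampling moves to the next day if the previous day's tablet was missed (Protocol 11.2.1). The accountability listing still shows each patient's data. All of this stands, and it bounds the size of the problem.

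It does not remove it. One could say that the closing visit is obviously meant to count. But SAP 4.6 includes the closing visit where it intends to, for MPV3 and EDV, and excludes it for the dose periods.

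A reader might infer more than the documents support:

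- *That every return falls in the next period, so that no by-period value exists for anyone.* Maintenance and EDV returns contradict this. The loss of maintenance rests on one reading of clause 2, which may mean only that earlier bottles are not counted. The SAP does not settle which.
- *That PD#25 can never be triggered.* Its overall arm works, as does period A for a withdrawal in dose A.
- *That making overall compliance missing after one unreturned bottle hides the less adherent patients.* Nothing in the documents links unreturned bottles to adherence, and leaving the value missing agrees with the no-imputation rule in SAP 4.10.

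**Conclusion.** The concern holds for dose finding. As written, compliance by dose and for the whole dose finding period is missing for essentially every patient who finishes the period. The down-titration period also has no usable value. Maintenance compliance is missing on the literal reading of the previous-period clause and normally calculable on the other. For completed dose periods, the by-period arm of PD#25 has no values.

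This assumes scheduled returns, one bottle set per visit interval, and the SAP 4.6 dates applied as written. A bottle handed back at an unscheduled on-site visit before the period closes could be an exception.

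The consequence is the loss of a descriptive adherence check at each dose; effects on the PK set or on any endpoint estimate are not shown. The Data Review Report cited in the SAP is dated 10-MAR-2022 and the final SAP 22-MAR-2022. If by-period values were reviewed for completed dose periods, they did not follow the written rule; if not, that part of the review was empty. The documents do not say which.

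**What to change.** In SAP 5.4.2:

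1. Credit each returned count to the period in which that bottle was dispensed, matching on bottle number, whatever the return date. Counting the closing visit as part of the period for returns gives the same result when bottles come back on schedule.
2. State that a bottle dispensed at MPV3 or EDV for down-titration belongs to the down-titration period, whichever day is recorded.
3. Delete the previous-period clause.
4. Set a period to missing only when one of its bottles is never returned.
5. Where one bottle covers two prescribed doses because nothing new was dispensed at down-titration, compute compliance over the combined interval against the sum of tablets prescribed at each dose, or set the separate periods to missing.
6. Leave the overall-compliance rule as it is.

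The report should also say which rule produced the by-period values considered at data review.

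The cost is a few sentences in the SAP and a merge by bottle number. Dispensed and returned bottle numbers are already in the eCRF, so no new data are needed. For a patient completing 200 mg who returns every bottle on schedule, this restores A, B, C, D and whole dose finding, and removes the doubt over maintenance.
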